4.3.3.4 Pharmacokinetics

Pharmacokinetic summaries will be based on the PK analysis set.

Post-dose concentrations where actual time deviates more than 10% from scheduled time will be excluded from summaries by planned time point.

Plasma concentrations of AZD9567 will be summarised by planned time point using n, counts of the number of subjects with results less than the lower limit of quantification (LLOQ), geometric mean, geometric mean +/- geometric standard deviation (GSD), geometric coefficient of variation (GCV), arithmetic mean, SD, CV, median, minimum and maximum.

PK parameters listed in Section 3.3 will be summarised using n, geometric mean, CV (%), arithmetic mean, SD, CV, median, minimum and maximum. For tmax, only median, minimum and maximum will be presented.

Plasma concentrations that are <LLOQ or if there are missing values (e.g. no result [NR]) will be handled as follows:

- Any values reported as no result or no sample will be excluded from descriptive statistics, inferential statistics and summary tables. However, data from subjects excluded from the PK analysis set will be included in the data listings.
- At a time point where less than or equal to 50% of the concentration values are non-quantifiable (NQ), all NQ values will be substituted with the LLOQ value, and all descriptive statistics will be calculated accordingly.
- At a time point where more than half (but not all) of the values are NQ, the geometric mean, geometric mean +/- GSD, GCV (%), SD, and CV (%) will be set to NC. The maximum value was reported from the individual data and the minimum and median were set to NQ.
- If all values are NQ at a time-point, no descriptive statistics will be calculated for that time-point. Not calculated (NC) will be written in the field for SD and CV% and NQ will be written in fields for mean, geometric mean, minimum, median and maximum

Three observations >LLOQ are required as a minimum for a plasma concentration or PK parameter to be summarised. Two values are presented as a minimum and maximum with the other summary statistics as NC.

Concentration data will be presented to the same number of significant figures as the data received from the bioanalytical laboratory; for PK parameters, the listings will be presented according to the following rules:

- Cmax – will be presented to the same number of significant figures as received from the bioanalytical laboratory
- tmax, t lower and t upper time limit – will be presented as received in the data, usually to 2 decimal places
- AUClast, t_{1/2}Z, CL/F, Vz/F, Rsq adj will be presented to 3 significant figures
- λz – will be presented to 4 significant figures
- λz, N – will be presented as an integer (no decimals)
- AUC(0-24)extr – will be presented to 2 decimal places

For PK concentration data all descriptive statistics will be presented to 4 significant figures with the exception of the minimum and maximum which will be presented to 3 significant figures.

For PK parameters data the descriptive statistics will be presented according to the following rules:

- Cmax, AUClast, t_{1/2}Z, CL/F, Vz/F – all descriptive statistics will be presented to 4 significant figures with the exception of the minimum and maximum which will be presented to 3 significant figures
- λz – all descriptive statistics will be presented to 5 significant figures with the exception of the minimum and maximum which will be presented to 3 significant figures
- tmax – all descriptive statistics will be presented as received in the data, usually to 2 decimal places

Individual plasma concentrations of AZD9567 will be plotted for each subject based on actual timepoint the sample was collected in linear and semi-logarithmic scale. NQ results will be plotted as the LLOQ for the linear scale and log(LLOQ) for the semi-logarithmic scale.

The geometric mean (+/-GSD) plasma concentrations of AZD9567 will be plotted by planned timepoint in linear and semi-logarithmic scale (no GSD bars). For mean plots, BLQ values will be handled as described for the summary tabulations; for individual plots plasma concentrations which are <LLOQ prior to the first quantifiable concentration will be set to a value of zero (linear plots only). After the first quantifiable concentration, any <LLOQ plasma concentrations will be regarded as missing.

Pharmacokinetic parameters will be listed.

A listing of plasma concentrations of AZD9567 including sample collection times as well as derived sampling time deviations will be provided.

4.3.3.5 Other exploratory outcomes

EULAR responses, DAS28 remission, clinically important change in DAS28 and low disease activity based on DAS28 score will be summarised separately by treatment group and visit to Day 28 using counts and percentages. No formal statistical testing will be done.

4.4 Missing primary and secondary variables

4.4.1 Missing DAS28 (CRP) components

DAS28-CRP will be set to be missing if one or more components as defined above are missing. Higher DAS28-CRP scores indicate more severe symptoms and greater functional impairment

4.4.2 Missing tender or swollen joints

The number of tender/swollen joints will be calculated by summing all joints checked to have tenderness/swelling present. If at least half but not all of the joints are evaluable, then the observed prorated joint count will be calculated instead. The prorated scores for TJC will be adjusted based upon the number of evaluable joints: the counted score will be multiplied by 68 then divided by the number of joints evaluated (excluding non-evaluable joints and any joints with a missing response). For example: if only 60 of the 68 joints are assessed to be evaluable at a visit, and 32 of those 60 are tender, the prorated joint count is $(32/60) \times 68 = 36.27$ (not 32) and it will be used in calculating the percent change from baseline in TJC. The same algorithm will be applied to the calculation of percent change from baseline in SJC with the exception that the counted score will be multiplied by 66 then divided by the number of joints evaluated. If less than half of the joints are evaluable, the number of tender/swollen joints is missing

This same algorithm will be used for the calculation of TJC and SJC based on 28 joints, which is part of the DAS28-CRP score.

4.4.3 Missing ACRxx components

At any visit, if one or more components are missing, such that a determination of ACR20 response cannot be made, then ACR20 will be set to missing. ACR20 will be set to missing for all visits for subjects with 0 SJC or 0 TJC at baseline. However, ACR20 will not be set to missing in cases where a determination of ACR20 response can be made based on the non-missing components.

In particular, in calculating ACR20:

- If $SJC66 \geq 20\%$ improvement and $TJC68 \geq 20\%$ improvement and if at least 3 of the 5 components are present, then:
 - if at least three are $\geq 20\%$ improvement, then ACR20 = 'Responder'
 - if at least 3 are $<20\%$ then ACR20 = 'Nonresponder'
 - else ACR20 is set to missing

- If $SJC66 < 20\%$ improvement or $TJC68 < 20\%$ improvement, then $ACR20 =$ 'Nonresponder'.
- If either $SJC66$ or $TJC68$ is missing and the nonmissing value $< 20\%$ improvement, then $ACR20$ is set to "Nonresponder".
- If either SJC or TJC is missing and the nonmissing value $\geq 20\%$ improvement, then $ACR20$ is set to missing.
- If SJC and TJC are both missing, then $ACR20$ is set to missing.

The same rules are followed in calculating $ACR50$ and $ACR70$, replacing 20% improvement with 50% and 70% , respectively.

Any subject with missing $ACRxx$, will be defined as "Nonresponder" for that visit.

4.5 Multiple Comparisons/Multiplicity

Not applicable.

4.6 Subgroups

Exploratory analyses may be performed where subgroups of interest have been identified and depending on the numbers of subjects within each subgroup.

4.7 Sensitivity analysis

A sensitivity analysis for the MMRM analysis of the primary endpoint will be performed using an ANCOVA model of change from baseline to Day 15 in DAS28 score with DAS28 score at baseline as covariate and country and treatment group as factors. The PROC GLM procedure in SAS will be used.

The LS-Means and 95% confidence interval will be presented by treatment group. The difference relative to prednisolone 20mg will be presented along with 95% confidence interval and p-value for two-sided comparison

4.8 Demographic, Dosing, and Safety and Tolerability data

There is no formal statistical analysis of safety and tolerability data required for this study. Demographic and other baseline disease characteristics, protocol deviations, concomitant medication, dosing, exposure, safety and tolerability data will be summarised and listed per AZ corporate CSRHLD reporting standard.

4.8.1 Subject disposition, important protocol deviations and analysis set

Subject disposition will be summarised for all subjects using the ENR analysis set. The number and percentages of subjects will be presented for the following categories: enrolled, randomised to study treatment, not randomised to study treatment (and reason), received study treatment, did not receive study treatment, completed study treatment, discontinued from

study treatment (either), discontinued from AZD9567/AZD9567 placebo treatment (and reason), discontinued from Prednisolone/Prednisolone placebo treatment (and reason), completed study and prematurely withdrawn from study (and reason). A subject will be enrolled and randomised into the study once all the inclusion/exclusion criteria are met as discussed in Section 3 in the latest version of the protocol.

Reasons for subjects not randomised will be obtained from the disposition eCRF, where randomisation code received is no.

Subjects who completed treatment are defined as subjects who completed in both AZD9567/AZD9567 placebo and Prednisolone/Prednisolone placebo groups.

Subjects who discontinued treatment are defined as subjects who discontinued treatment in either treatment group AZD9567/AZD9567 placebo or Prednisolone/Prednisolone placebo.

Reasons for discontinuation of study treatment and prematurely withdrawn from study will also be listed including the study day of treatment discontinuation.

Important protocol deviations and analysis sets will be tabulated using the FAS only on important protocol deviations. Important protocol deviations will also be summarised and listed.

The number and percentage of subjects included and excluded from each analysis set will also be presented, including the reason for exclusion from each analysis set. Listings of subjects excluded from each analysis set (SAF, FAS, PP, PK) will be provided.

4.8.2 Demographic and baseline characteristics

Demographic and baseline characteristics will be summarised based on the all subject analysis set FAS.

Demography data such as age (years), age group (years) (<18, 18-40, 41-65, >65), sex, race, and ethnicity will be summarised and listed.

Various baseline characteristics of the subjects will also be summarised and listed. These include weight, height and body mass index (BMI), disease characteristics, and extent of disease at baseline.

Disease characteristics are obtained from the rheumatoid arthritis history eCRF page. The following will be summarised using frequencies and percentages:

- Presence of radiological erosions (Yes, No)
- Rheumatoid factor positive (Yes, No)
- Current functional capacity class (Class I, Class II, Class III, Class IV)
- Previously treated with TNF α antagonist (Yes, No)
- Reason for TNF α discontinuation (No response, Initial response but subsequent loss of response, Adverse effect/Intolerance, Other)

Years since onset of RA symptoms will be summarised using summary statistics and is calculated relative to informed consent date:

$$\begin{aligned} \text{Years since onset of RA symptoms} \\ = (\text{informed consent date} - \text{Onset of RA symptoms date} + 1) / 365.25 \end{aligned}$$

Years since RA diagnosis will be summarised using summary statistics and is calculated relative to start date:

$$\begin{aligned} \text{Years since RA diagnosis} \\ = (\text{informed consent date} - \text{RA first diagnosed date} + 1) / 365.25 \end{aligned}$$

Details on partial date handling for onset of RA symptoms date and RA first diagnosed date can be found in Appendix D.

Age will be summarised as collected on the eCRF and will not be rederived.

BMI will be calculated as the ratio of the subject's baseline weight (in kilograms) to the square of the subject's height (in metres): $\text{BMI} = \text{kg}/\text{m}^2$.

4.8.3 Prior, concomitant, and post-discontinuation medications and therapies

Concomitant medications and therapies tabulations will be summarised based on the SAF.

Disease-related and other medications and therapies will be classified by the AstraZeneca designee according to the latest version of the World Health Organization (WHO) Drug Dictionary and they will be categorised as follows:

- Prior medications, defined as those medications taken prior to the first AZD9567/Prednisolone dose.
- Concomitant medications, defined as those medications taken during the course of the treatment period (i.e., from the day of the first AZD9567/Prednisolone dose up to the day of the last AZD9567/Prednisolone dose). A medication started prior to the first AZD9567/Prednisolone dose that is still used during the treatment period will be identified as both prior and concomitant.
- Post-discontinuation medications, defined as those medications started after the last AZD9567/Prednisolone dose.

If a medication has a missing start date then unless the stop date of the medication indicates otherwise, this medication will be considered as both prior and concomitant. Similarly, if a medication has a partial start date, then unless the partial start date or the stop date indicate otherwise, this medication will be considered as both prior and concomitant. See Appendix D Partial and missing date conventions for additional details.

All concomitant medications will be summarised by WHO Drug anatomic therapeutic chemical (ATC) level 4 classification and generic term. Prior and post-discontinuation medications will be listed only.

4.8.4 Medical history

Medical history and relevant surgical history will be coded by the AstraZeneca designee using the latest version of the MedDRA and will be summarised and listed.

4.8.5 Exposure

Exposure data will be summarised and listed for the SAF.

Total treatment duration and compliance will be summarised and listed. In addition, interruptions and compliance are not taken into account for duration of exposure. Reason for dose discontinuation will also be summarised and listed.

- Duration (days):
(End date - start date) + 1.
- Total treatment exposure (months):
[(End date – start date) + 1]/12
- Actual number of study treatment taken:
Total number of bottle/capsules dispensed - total number of bottle/capsules returned.

Duration for study treatment will summarised cumulatively in the following categories:

- Treatment received more or equal to 1 day: Treatment duration ≥ 1
- Treatment received more or equal to 15 days: Treatment duration ≥ 15

Subjects taking $\geq 75\%$ and $\leq 125\%$ of planned study treatment are considered compliant. The percentage treatment compliance will be calculated as the actual number of study treatment taken relative to the expected number of study treatment to be taken.

- Expected number of study treatment taken:
AZD9567/AZD9567 placebo: 1 bottle x 15 days = 15
Prednisolone/Prednisolone placebo: 4 capsules x 15 days = 60
- Percentage treatment compliance:
(Actual number of study treatment taken) / (Expected number of study treatment taken) x 100

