7.2 Dose and treatment regimens

A total of 40 eligible patients will be randomly assigned 1:1 to the study treatment. This will be managed via IWRS. The dose of IP, AZD9567 40 mg and prednisolone 20 mg, will be

taken once daily (in the morning) for 14 days. Detailed instructions are provided in the Handling instructions each patient will be provided with in local language. The first dose of IMP will be taken at the clinic after the baseline assessments have been performed on Visit 2. Also at the end of treatment visit, Visit 5, the IMP should be taken at the site to allow for a pre dose blood sample to be drawn for PK analyses. As the IMP has different formulations, double dummy technique is applied. Each patient will therefore take both oral suspension and 4 capsules of prednisolone/placebo on a daily basis for 14 days. The oral suspensions of AZD9567 and placebo are not taste neutral. This information will be included in the Patient Informed Consent form. Opening aids for the IMP bottles will be supplied by AstraZeneca and will be described in the Handling instructions.

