1. STUDY DETAILS

1.1 Study objectives

1.1.1 Primary objective

The primary objective of this study is to assess the efficacy of AZD9567 40 mg, compared to Prednisolone 20 mg in subjects with active rheumatoid arthritis (RA) in spite of stable treatment with conventional and/or subcutaneous (s.c)/ intravenous (i.v.) biological disease-modifying anti-rheumatic drugs (DMARDs) by assessment of:

- Change from baseline (CFB) in 28 joints Disease Activity Score (DAS28) using C-reactive protein (DAS28 - CRP) after 14 days of treatment at Day 15.

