1.2 Study design

This is a Phase 2a, randomised, double-blind, double dummy, parallel study to assess the efficacy, safety and tolerability of AZD9567 40mg compared to Prednisolone 20 mg in subjects with active RA in spite of stable treatment with conventional or biological DMARDs.

At Visit 1 (screening visit) eligible subjects will be identified. Subjects will be asked to provide informed consent after which screening assessments will be performed.

At Visit 2, eligible subjects with established RA and moderate to high disease activity as defined by ACR Guidelines (DAS28 > 3.2) will be randomised in a ratio 1:1 to take either AZD9567 40 mg or Prednisolone 20 mg for 14 days once daily. Since this study is double-blind and AZD9567 and Prednisolone are different formulations (oral suspension and capsules respectively), all subjects will have to take both formulations every day (active AZD9567 + placebo to Prednisolone or placebo to AZD9567 + active Prednisolone).

[figure not shown]
A telephone call to check subject well-being will be termed Visit 3.

Visit 4 will occur approximately 7 days after Visit 2, and Visit 5, which is the end-of-treatment visit, will occur approximately 14 days after Visit 2.

A follow-up visit (Visit 6) will be performed approximately 14 days after last study treatment dose (at Visit 5) to ensure the safety and well-being of subjects.

For more information regarding the visits and time windows refer to the study flowchart, [Figure 1](#).

Figure 1 Study flow Chart

R: Randomised to study treatment

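### SAP 4.8.5 converts exposure from days to months by dividing by 12, which overstates months of exposure about 2.5-fold for every treated subject

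*SAP*

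**What the plan says.** SAP 4.8.5 (Exposure) applies to the safety analysis set, that is, all randomised subjects with at least one dose. It gives two lines for length of exposure. The first, in days, is end date minus start date plus one. The second, labelled as months, takes that same expression and divides by twelve: "End date – start date) + 1]/12". The section then sets duration categories in days (at least 1, at least 15) and a compliance percentage based on bottles and capsules.

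SAP 4.8.2 (Demographic and baseline characteristics) shows how the SAP converts days elsewhere. Years since symptom onset and years since diagnosis are both a day difference plus one, divided by 365.25.

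On the number of dosing days:

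- SAP 4.8.5 expects "1 bottle x 15 days = 15" for the suspension and "4 capsules x 15 days = 60" for the capsules.
- SAP 1.2 describes "AZD9567 40 mg or Prednisolone 20 mg for 14 days once daily".
- SAP 1.1.1 places the primary assessment "after 14 days of treatment at Day 15".
- Protocol 7.2 says the dose is "taken once daily (in the morning) for 14 days", and in the same section: "Also at the end of treatment visit, Visit 5, the IMP should be taken at the site". Protocol Table 1 puts Visit 5 at Day 15 ± 1.

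**The concern.** The numerator of the months formula is a count of days, as the line before it in the SAP makes plain. A divisor of 12 turns months into years; it does not turn days into months. If the formula is programmed as written, the exposure table and listing will show more than one month of treatment for anyone treated for 13 days or longer, in a study whose treatment period is two weeks. The months line will also contradict the days line beside it.

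Length of exposure is part of the context for reading the safety tables here. The protocol describes the study as the first in patients (section 1.1) and says that 5 days is the longest AZD9567 regimen so far in a clinical study (section 4.2). A line implying more than a month of dosing would misdescribe that experience.

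The 14/15-day wording is a lesser matter. The compliance denominator rests on 15 dosing days, while other passages say 14.

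**Working it through.** **Inputs**

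- Day count D = end date − start date + 1 (SAP 4.8.5).
- Months as the SAP defines them: D/12 (SAP 4.8.5).
- Year length: 365.25 days (SAP 4.8.2). The SAP states no month length; 365.25/12 is carried over from this as an assumption.
- The SAP gives a formula and no worked value, so there is no printed figure to reproduce.

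**Month length and factor**

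- Days per month = 365.25/12 = 30.4375.
- Overstatement = (D/12) ÷ (D/30.4375) = 30.4375/12 = 2.536, or 2.54. D cancels, so the factor is the same at every duration.

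**Results by duration**

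| Days | SAP formula, D/12 | D/30.4375 |
|---|---|---|
| 1 | 0.08 | 0.03 |
| 7 | 0.58 | 0.23 |
| 13 | 1.08 | 0.43 |
| 14 | 1.17 | 0.46 |
| 15 | 1.25 | 0.49 |
| 16 | 1.33 | 0.53 |

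**Sensitivity to the month length**

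- 28 days: 28/12 = 2.33
- 30 days: 30/12 = 2.50
- 365/12 days: 30.4167/12 = 2.53
- 31 days: 31/12 = 2.58

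**Secondary check: does 14 or 15 dosing days matter for compliance?**

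The compliant range is 75% to 125% of the expected count.

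| Product | Expected count | 75% to 125% | Compliant counts |
|---|---|---|---|
| Bottles, 15 days | 15 | 11.25 to 18.75 | 12–18 |
| Bottles, 14 days | 14 | 10.5 to 17.5 | 11–17 |
| Capsules, 15 days | 4 × 15 = 60 | 45 to 75 | 45–75 |
| Capsules, 14 days | 4 × 14 = 56 | 42 to 70 | 42–70 |

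The class therefore changes only in these cases:

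- at 11 bottles (11/15 = 73.3%, 11/14 = 78.6%);
- at 18 bottles (18/15 = 120.0%, 18/14 = 128.6%);
- at 42–44 or 71–75 capsules.

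A subject who takes every dose through a Visit 5 anywhere in its window takes 14 to 16 doses. Against 15 this scores 14/15 = 93.3% to 16/15 = 106.7%, always compliant.

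**The case against.** The case for leaving this alone is that nothing depends on it. The days line is correct, the duration categories are in days, and compliance uses bottles and capsules. The adverse event summaries are counts and percentages with no person-time rates, and no efficacy model includes exposure. A reader who saw 1.25 months beside 15 days would probably recognise a slip. All of this is true. It limits the consequence, but it does not make the formula right: the SAP instructs the programmer to produce a wrong number for the whole safety set.

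A second objection is that 2.54 depends on a month length the SAP never states, since the 365.25 in section 4.8.2 is a year conversion for disease duration. That stands as a caveat on the second decimal. Any plausible month length still gives 2.33 to 2.58.

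Third, the SAP appendices, including the one on date conventions, and the corporate reporting standard named in SAP 4.8 were not available for this check. It can be said only that nothing in the available text corrects the divisor. A general convention elsewhere would still conflict with the explicit formula.

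On the dosing days, SAP 1.1.1 can fairly be read as 14 daily doses followed by an assessment on Day 15, which is compatible with a further dose at that visit. The real tension is between the 14-day statements in protocol 7.2 and SAP 1.2, and the Visit 5 dose and 15-day count in protocol 7.2 and SAP 4.8.5. SAP 1.1.1 belongs in the reconciliation only so that the count is stated consistently.

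**Conclusion.** The point holds. The months formula in SAP 4.8.5 has a unit error that overstates exposure 2.54-fold for every treated subject with known start and end dates, taking a month as 365.25/12 days (2.33 to 2.58 for months of 28 to 31 days). The effect is confined to one descriptive line and does not touch the primary result, the safety counts or compliance. It should be corrected because it is certain, visible and nearly free to fix.

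The 14/15-day discrepancy is secondary. It is an inconsistency of wording with little practical effect, and no position is taken here on which number of dosing days is right.

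**What to change.** In SAP 4.8.5, replace the divisor 12 with 30.4375 (365.25/12, in line with the 365.25-day year in SAP 4.8.2). Alternatively, delete the months line and report exposure in days only, which is enough for two weeks of treatment. Either way the cost is one change in the SAP and the matching program line, with no new data.

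Separately, reconcile the number of dosing days across protocol 7.2 and SAP 1.1.1, 1.2 and 4.8.5, so that the compliance denominator rests on one stated number. This needs a clarification in the SAP and, if protocol 7.2 is changed, a protocol text change.
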